The natural history of TAAs, including aneurysms of the DTA, is one of progressive enlargement and rupture, and rupture is almost invariably fatal. An early study on the natural history reported that over 90% of patients sustained aneurysm growth during the period of observation.⁹ Risk of rupture has been found to be correlated to aneurysm size and growth rate.⁵ An average growth rate of 0.19 cm per year has been observed in aneurysms of the DTA in the past.¹⁰ An aneurysm diameter of 6-cm has been generally considered the urgent point of the risk for rupture.

Degenerative change of the aortic wall is the cause of most aneurysms of the DTA. Medial degenerative disease is responsible for most fusiform aneurysms of the DTA. The smooth muscle cells and elastic laminae in the media are replaced by cystic spaces filled with mucoid material, which produces progressive weakening and dilatation of the aortic wall, with eventual aneurysm formation and subsequent complications such as rupture. Arteriosclerosis is a process that primarily involves the aortic intima, which accounts for 80% of the aneurysms found in the thoracic aorta. The intima degenerative change is characterized by raised atheromatous intimal plaques consisting of a lipid core and fibrous cap, which eventually compromises blood flow and weaken the vessel wall. TAAs that are caused by atherosclerosis are frequently saccular, and could result from penetrating atherosclerotic ulcers. Are Current available treatment includes medical treatment, open surgical repair and endovascular stent-graft repair.

Standard surgical treatment involves a thoracotomy, aortic clamping to re-section the aneurysmal segment and replacement using a Dacron graft. Endovascular stent graft repair consists of transfemoral or iliac introduction of the device. When the stent graft device is deployed and expanded within the aneurysmal blood vessel, it creates a new aortic lumen for the blood flow, excluding the aneurysm sac from blood flow while maintaining perfusion to the lower body. Studies comparing open surgical repair versus endovascular repair concluded that the latter offers a less invasive, less expensive alternative, a decrease in mortality and morbidity in highrisk patients, associated with shorter hospital stay and quicker return to normal activities after surgery. 13,14

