- Screening CT or MRA with contrast of the chest, abdomen and pelvis completed within four months prior to the index procedure. This will be used to visualize and assess the characteristics, length, and diameters of the DTAA and the surrounding anatomy.

Screening/ Baseline Assessments:

After the subject has voluntarily signed and dated the Informed Consent Form, the subject will be considered a study candidate. If a subject does not sign the Informed Consent Form, then no further study specific screening procedures can occur.

Collection of screening and baseline information will take place only after the subject has given voluntary, documented informed consent and will include the following:

- Subject demographics
- Medical history
- · Current health status
- Risk factors
- ASA Physical Status Classification
- EQ-5D Questionnaire

Screening CT/MRA images will be reviewed by the investigator to confirm eligibility. The imaging will also be sent to a core lab to assess the anatomical inclusion/exclusion requirements. An Independent Physician Reviewer (IPR) will review screening CT/MRA images to confirm eligibility. Approval by the IPR must be obtained prior to a subject's actual inclusion in the study. The decision of the IPR will be communicated to the investigational site by the Sponsor. Those subjects who sign and date the Informed Consent, meet all study eligibility criteria, and are approved by the IPR will be eligible for inclusion in the study. Subjects that are not approved by the IPR are considered screen failures and will not be followed per study protocol.

Subjects who do not qualify for enrollment will be documented as ineligible on the Screening and Enrollment log.

Enrollment:

Those subjects who sign and date the informed consent document, meet all of the study eligibility criteria, and are approved by the IPR will be eligible for inclusion into the Valiant Evo US Clinical Trial. The subject will only be considered enrolled when arterial access is established and an attempt to introduce the Valiant Evo Thoracic Stent Graft is made.

Enrolled subjects will be documented on the electronic Screening and Enrollment Log. Subjects who are enrolled, but not implanted with the device, will be followed through the 1 month follow-up only.

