1 Month (± 15 days)	15	30	45
6 Month (183 ±30 days)	153	183	213
12 Months (365 ±60 days)	305	365	425
24 Months (730 ±60 days)	670	730	790
36 Months (1095 ±60 days)	1035	1095	1155
48 Months (1460 ±60 days)	1400	1460	1520
60 Months (1825 ±60 days)	1765	1825	1885

Table F-1: Post-Implantation Follow-Up Visit Schedule and Windows

At all required follow-up visits subjects will undergo the following assessments and procedures:

- Physical Examination
- Chest CT/MRI with contrast
- EQ-5D questionnaire
- Adverse event assessment

A CT/MRI with contrast acquired at discharge (or before day 15) due to medical necessity may be used to meet the 1-month follow-up visit CT/MRI requirement if a CT/MRI with contrast cannot be obtained within the 1-month follow-up window due to the subject's health status based upon physician discretion.

If conversion to open repair is required during the follow-up period, then the subject will be followed for 30 days after the conversion, at which time the subject will be exited from the study.

F.3 Data collection requirements

Clinical data will be collected preoperatively to establish eligibility, at baseline, during the index procedure, throughout the hospital stay, and postoperatively at the required (and any interim imaging) follow-up visits described in Section F.2. The data collection schedule is summarized in Table F-2. Imaging source data will be sent to a Core Lab for analysis up to the 12-month follow-up visit. Any interim imaging of the stent graft region but not linked to a study visit should be recorded on the Interim Image eCRF (e.g. imaging performed as standard of care beyond the protocol required time points and/or when performed further to any issue observed at previous imaging Follow-up).

Imaging source data beyond 12-months post-index procedure will not be sent to the Core Lab for analysis. Instead, study sites are to report the results of the imaging performed as standard of care and in line with local and site requirements directly on the e-CRF. Routinely acquired images may be required for adjudication purposes in case of CEC adjudication or any other safety event.

Study data will be collected using electronic case report forms (eCRFs) as described in Section G.1. Clinical investigators must electronically review and approve all eCRFs. Medtronic monitors will perform source document verification of the eCRFs. The monitoring strategy will be defined in the monitoring plan.

Table F-2: Data Collection Schedule

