Secondary procedure	Any endovascular or surgical procedure performed following the completion of the operative initial implantation procedure (thus on subsequent occasion after final closure of the last artery access site) which involves the targeted vascular segment treated by the Valiant Evo Thoracic Stent Graft System in which there is either manipulation of the existing Valiant Evo Thoracic Stent Graft, implantation of any additional stent graft devices or manipulation of covered branch(es) by implanted stent grafts.
Conversion to open surgery	Primary Conversion : Conversion from endovascular to open repair required at the time of the original procedure, to treat the lesion intended to be treated with the Valiant Evo Thoracic Stent Graft System.
	Secondary Conversion : Conversion from endovascular to open repair required at a time beyond the initial endovascular procedure, to treat the lesion originally treated with the Valiant Evo Thoracic Stent Graft System.
Thoracic Aortic Aneurysm rupture	Rupture or perforation of the targeted thoracic aneurysmal sac as detected by angiography, CT scan, or direct observation at surgery or autopsy.

Term	Definition
	Aneurysm rupture should be reported as either procedure- related aneurysm rupture (i.e., perforation of the aneurysm during the course of the implantation procedure) or as a late aneurysm rupture that follows device deployment.
	Excluded are aneurysms in anatomic areas other than the targeted segment treated by the Valiant Evo Thoracic Stent Graft System.
Aneurysm expansion	Aneurysm maximum diameter increase > 5 mm as compared to the 1- month contrast enhanced imaging measurements
Stent graft migration	Evidence of proximal or distal movement of the stent graft (>10 mm) relative to fixed anatomic landmarks (e.g. supra aortic trunks, coeliac trunk), which is not due to remodeling of the subject's vasculature.
	The 1-month imaging will be used as the baseline for this determination.
Loss of stent graft patency	Defined as a 100% complete blockage (occlusion) of the lumen diameter of any implanted stent graft component(s) as evidenced by CT, angiography, ultrasound, or other appropriate imaging modality, and/or operative pathological analysis.
Endoleak	Defined by the presence of contrast-enhanced blood outside the lumen of the endoluminal graft but within the aneurysm sac. Endoleaks are classified as follows:
	Type I a – Leak at the proximal graft attachment site

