7.2. General Methodology

In general, qualitative parameters will be described by their distribution frequencies; quantitative parameters will be described by their mean, standard deviation, minimum, maximum, median, and number of subjects with assessable data.

For events such as adverse events (AE), deaths and secondary procedures, that can occur or are observed at any time during the study, no time window will be applied. For such events, an event that occurs "within 1 month or 30 days" is an event that takes place between Days 0 to 30, inclusive. Similarly, an event that occurs "within 12 months or 365 days" is an event occurring between Day 0 to Day 365, inclusive. Date of event onset will be used to determine when the event occurred. Day 0 is referring to the day of index procedure.

For image-based assessments, such as stent-graft endoleak, patency, and other observations, the following time windows will be applied for by-visit data summaries:

Study Visit	Target Day	Time Window
Implant	Day 0	Day 0
1 Month	Day 30	1 – 90 days
6 Months	Day 183	91 – 304 days
12 Months	Day 365	305 – 548 days
24 Months	Day 730	549 – 913 days
36 Months	Day 1095	914 – 1278 days
48 Months	Day 1460	1279 – 1643 Days
60 Months	Day 1825	1644 – 2009 days

Table 3: Time Windows for Statistical Analyses

Unless otherwise specified, if different type of images are used and have different finding in the same time window, the imaging technique and sensitivity matrix (CIP Appendix L.3, also see Table 4 below) will be applied. Finding from higher visibility image will be used for analysis. If there are two or more assessments in the same time window, then the assessment closest to the target day will be used in the analysis of event rate at a given time point.

Valiant Evo US Clinical Trial Statistical Analysis Plan

Version 2.0 Nov 1, 2017

This document is electronically controlled. Printed copies are considered uncontrolled.

Anatomy/Stent Graft Issue Detected	CT with contrast	CT without contrast	MRI with contrast	MRI without contrast	Angiogram/, Aortogram, and Arteriogram
Diameter and Length	1	2	1	2	3
Stent graft migration	1	2	1	2	2-3
Stent graft fracture	2	3	2	3	2-3
Stent graft kinking	2	3	2	3	2-3
Collapse of stent graft	2	3	2	3	2-3
Stent graft twisting	2	3	2	3	2-3
Stent graft patency	1	4	1	4	2-3
Endoleaks	1	4	1	4	2-3
False lumen perfusion	1	4	1	4	2-3
Occlusion	1	4	1	4	2-3
Stenosis	1	4	1	4	2-3
Stent Graft Fabric Defect	1	4	1	4	2-3

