- All AEs within 183 days including:
 - \circ MAEs
 - o SAEs
- Secondary procedures within 183 days
- Loss of stent graft patency within 6 months based on imaging findings
- Endoleaks at 6 months based on imaging findings

Valiant Evo US Clinical Trial Statistical Analysis Plan Version 2.0 Nov 1, 2017

This document is electronically controlled. Printed copies are considered uncontrolled.

- Stent graft migration at 6 months as compared to 1-month imaging
- Aneurysm expansion > 5mm at 6 months based on imaging findings relative to the 1-month visit

12-month Secondary Endpoints

The following secondary endpoints will be evaluated:

- All-cause mortality within 365 days
- Aneurysm-Related Mortality within 365 days
- MDEs within 365 days
- All AEs within 365 days including:
 - o MAEs
 - o SAEs
- Secondary procedures within 365 days
- Loss of stent graft patency within 12 months based on imaging findings
- Endoleaks at 12 months based on imaging findings
- Stent graft migration at 12 months as compared to 1-month imaging
- Aneurysm expansion > 5mm at 12 months based on imaging findings relative to the 1-month visit

Secondary endpoints are to be assessed beyond 12 months. The following secondary endpoints are to be evaluated at 24, 36, 48, and 60 months:

- All-cause mortality
- Aneurysm-Related Mortality
- MDEs
- All AEs and SAEs
- Secondary procedures
- Loss of stent graft patency based on site reported imaging findings
- Endoleaks based on site reported imaging findings

Valiant Evo US Clinical Trial Statistical Analysis Plan Version 2.0 Nov 1, 2017

This document is electronically controlled. Printed copies are considered uncontrolled.

- Stent graft migration as compared to 1-month imaging
- Aneurysm expansion > 5mm based on site reported imaging findings relative to the 1-month visit

Health-related quality of life outcomes are to be assessed at all scheduled follow-up visits using the EQ-5D questionnaire.

Stent graft migration will be determined by the core lab or site imaging case report from (CRF). Core lab assessment and site reported result will be analyzed separately. Aneurysm expansion will be calculated. When 1-month image is not available, the latest image taken prior to 1-month will be used for calculation.

Descriptive statistical analyses will be performed on secondary endpoints. No inferential statistical analysis is planned for secondary endpoints.

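### If the 1-month scan is missing, the SAP lets a pre-implant image become the baseline for aneurysm expansion, contrary to the protocol definition

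*SAP*

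**What the plan says.** Protocol Appendix L.2.1 defines expansion as "Aneurysm maximum diameter increase > 5 mm as compared to the 1- month contrast enhanced imaging measurements". The endpoint lists in Protocol C.2.2 and SAP 7.9 repeat the 1-month reference at 6, 12, 24, 36, 48 and 60 months. The protocol definition has no substitute baseline.

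SAP 7.9 says that expansion will be calculated and adds: "When 1-month image is not available, the latest image taken prior to 1-month will be used for calculation". It sets no condition on modality, contrast or timing relative to implant.

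Two windows could define the 1-month image:
- Protocol Table F-1 sets the 1-month visit at Days 15–45.
- SAP Table 3 sets the 1-month analysis window at Days 1–90, introduced with "the following time windows will be applied for by-visit data summaries".

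The images that could exist before the 1-month scan are:
- Screening (Protocol F.1): "Screening CT or MRA with contrast of the chest, abdomen and pelvis completed within four months prior to the index procedure". It also goes to the core lab.
- The Day 0 completion angiogram (Protocol F.2.1), normally not sent to the core lab (Table F-2, footnote f).
- An early post-implant scan (Protocol F.2.4): "A CT/MRI with contrast acquired at discharge (or before day 15) due to medical necessity may be used to meet the 1-month follow-up visit" imaging requirement, if the subject's health prevents a scan in the window.
- Unscheduled scans (Protocol F.3): "Any interim imaging of the stent graft region but not linked to a study visit should be recorded on the Interim Image eCRF".

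**The concern.** Expansion is meant to show whether the sac keeps growing after the graft has excluded it. That is why the protocol starts the clock at a post-implant scan. A baseline from before implant answers a different question, because the change since then includes whatever the untreated aneurysm did while the patient waited and whatever the sac did in the first weeks after implant.

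Subjects with such a baseline would be counted in the same rates as subjects measured from the 1-month scan, without being identified. SAP 7.9 makes the core-lab readings the main imaging result for the regulatory submissions, and the same baseline carries through to 60 months. Substituting an earlier scan for a missing one also sits uneasily with SAP 7.4, which rules out imputation except for the onset date of an adverse event or death.

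**Working it through.** The documents give no expansion rate, power or sample size for this endpoint, so there is no stated figure to reproduce. The check has three parts.

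**1. Which image does the substitute rule select?**

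| Scan day | Under Days 1–90 (SAP Table 3) | Under Days 15–45 (Protocol Table F-1) |
|---|---|---|
| Before Day 0 (screening) | Substitute candidate, pre-implant | Substitute candidate, pre-implant |
| Day 0 (completion angiogram) | Substitute candidate | Substitute candidate |
| Days 1–14 (discharge or interim) | Already the 1-month image | Post-implant; can serve as substitute, or as the 1-month image under F.2.4 |
| Days 15–45 | 1-month image | 1-month image |
| Days 46–90 | 1-month image | After the window |

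Under Days 1–90, only the screening CT/MRA and the Day 0 angiogram are left. The imaging matrix (Protocol L.3, SAP Table 4) grades contrast CT and contrast MRI 1 for diameter and angiography 3, the not-very-visible grade. The screening scan is therefore the practical substitute, above all for the core lab, which holds it. Under Days 15–45 the substitute is post-implant if a Day 1–14 scan exists. If none exists, it is again the screening scan or the angiogram.

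**2. What does a screening baseline measure?** Let G be the growth from screening to implant, E the change from implant to 1 month, and L the change from 1 month to the follow-up visit.

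- Protocol definition: event if L > 5 mm.
- Screening baseline: event if G + E + L > 5 mm.
- Error in the measured change: G + E.

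G is positive in a growing aneurysm. E can have either sign. If the sac shrinks by more than G in the first month, the error is negative and true later expansion can be missed.

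**3. How large is G?** G = annual growth × months from screening to implant ÷ 12, assuming steady growth up to implant. Inputs:
- mean growth from Protocol B.1: "An average growth rate of 0.19 cm per year has been observed in aneurysms of the DTA in the past", i.e. 1.9 mm/year;
- 5 mm/year, the minimum under the entry criterion for aneurysms below 50 mm (Protocol D.1);
- 10 mm/year, an assumed high value that is not in the documents;
- a gap of up to 4 months (Protocol F.1).

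| Growth rate | 1-month gap | 4-month gap | 4-month G as share of 5 mm |
|---|---|---|---|
| 1.9 mm/year | 0.16 mm | 1.9 × 4/12 = 0.63 mm | 12.7% |
| 5 mm/year | 0.42 mm | 5 × 4/12 = 1.67 mm | 33.3% |
| 10 mm/year (assumed) | 0.83 mm | 10 × 4/12 = 3.33 mm | 66.7% |

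With a 4-month gap, the post-implant change (E + L) that counts as an event falls from more than 5 mm to more than 5 − 0.63 = 4.37 mm at the mean rate, and to more than 5 − 1.67 = 3.33 mm at 5 mm/year.

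**The case against.** **The substitute need not be pre-implant.** A reader might infer that the rule always selects a pre-treatment scan. The documents do not support that. The SAP introduces Days 1–90 for visit summaries and then uses the analysis windows for imaging event rates; it never says that they select the expansion baseline. Under the Day 15–45 visit window, a discharge or interim scan on Days 1–14 could be the substitute, and the sentence can be read as carrying out the allowance in Protocol F.2.4. Even under Days 1–90, the completion angiogram follows deployment. This stands and limits the claim to what the rule permits and usually produces. It does not remove the conflict: on either window, a subject with no early post-implant CT/MRI can be given the screening scan.

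**The rule need not inflate expansion.** This also stands. G pushes the rate up, early shrinkage pushes it down, and the documents do not settle the net effect.

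**The number affected cannot be derived.** A reader might take 13 subjects (100 enrolled minus 87 evaluable) as those without a 1-month scan, or 63 as the 12-month denominator. Those are evaluability figures for the 30-day composite endpoint and the 1-year device-event endpoint. Imaging rates use subjects with readable images. An affected subject must lack a 1-month scan yet have a readable later one. The documents give no such count, and it may be zero.

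**The stakes are limited.** Expansion is descriptive, with no inferential test, and the 30-day primary test is untouched. At the mean growth rate the added amount is about one eighth of the threshold.

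**Leaving subjects out is itself a missing-data choice.** Protocol F.2.4 recognises that ill health can prevent the scan, so exclusion may be informative. The fix has to allow for this.

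**Conclusion.** The point holds in a limited form. SAP 7.9 permits a baseline that the protocol definition does not, and following the rule as written can misclassify subjects in either direction. The baseline can be a pre-implant scan and, under the Days 1–90 window, usually would be the screening CT/MRA.

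The pre-implant growth folded in is at most about 0.6 mm at the protocol's mean rate and about 1.7 mm at 5 mm/year. Both figures assume a full four-month gap and steady growth. Shorter gaps give less, and growth faster than 5 mm/year gives more. Early sac change is added on top and is not quantified in the documents.

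The effect on the reported rate cannot be stated without the number of affected subjects. For scale only, one reclassified subject in a denominator of all 100 planned subjects would move the rate by 1/100 = 1.0 percentage point. The point does not touch the primary endpoint or its power. It is a modest SAP–protocol conflict that should be corrected because the correction is simple.

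**What to change.** Replace the sentence in SAP 7.9 with a rule that does the following:

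1. Names the single window that defines the 1-month image for the expansion baseline. The choice has a price either way: Days 1–90 would accept a scan as late as Day 90 as baseline, while Days 15–45 would leave more subjects relying on the early-scan allowance or without a baseline.
2. Limits the baseline to a post-implant contrast-enhanced CT or MRI. An early post-implant scan accepted under Protocol F.2.4 qualifies. A pre-implant scan or the Day 0 angiogram does not.
3. Treats subjects with no such image as not assessable for expansion, leaves them out of numerator and denominator, and reports how many there are. Table 6 defines the denominator by a readable follow-up image alone, so for expansion it must also require a qualifying baseline.
4. Shows the result with the screening scan as baseline for those subjects as a labelled sensitivity analysis, because a missing 1-month scan may reflect poor health.
5. Applies the same rule to core-lab and site-reported expansion from 6 to 60 months, including the cumulative estimates.

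The cost is a short SAP edit, a small programming change and a slightly smaller denominator on a descriptive secondary endpoint. No new data collection is needed.
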